15.0 Appendices	

## **1. Abstract**

Classic bladder exstrophy is a complex birth defect that involves malformations of the genitourinary and musculoskeletal systems. This defect occurs in approximately 1:30,000 to 50,000 live births, and occurs more often in males than females [1]. The abdominal wall musculature fails to mature properly in the midline of the body leaving the bladder literally splayed open on the anterior surface of the neonate. Additionally, the urethra is completely open (epispadias) and the entire penis has failed to roll into a tube. The pubic bones are widened and have also failed to fuse properly in the midline. This birth defect, while extensive, is surgically correctable with a multi-stage operative plan over the child's formative years. Initially within a few days of life, the bladder and abdominal wall undergo closure. This is often accomplished with the use of pelvic osteotomies, which leave the child with external fixation devices postoperatively. The fixator devices are removed after 4-6 weeks of pelvic immobilization. The second stage involves early repair of the epispadiac penis. If the bladder grows to a sufficient volume, then the child undergoes a continence procedure around age 5 that allows for volitional voiding. Some children's bladders grow appropriately and others fail to grow appropriately. If the bladder does not sufficiently grow, then additional and considerably more complex continence procedure and bladder augmentation are required to make the child continent[2].

Much of the long-term success of these operations depends on the initial closure. Several studies have demonstrated that a key to successful initial closure involves deep dissection of the pelvic floor so that the bladder can be placed in the most posterior and inferior position possible [3-5]. Oftentimes, the need for repeat closure of the abdomen is required if the initial surgeon failed to properly dissect deep enough into the child's pelvic floor. Many surgeons are unfamiliar with the complex anatomy and are unable to verify that they have properly reached the true pelvic floor during this initial surgery. This often leads to failed closures, which result in poor continence rates later in life [2].

It is our hypothesis that the use of intraoperative stereotactic imaging will help verify where the surgeon is during his or her dissection during closure of bladder exstrophy. We anticipate that successful use of stereotactic imaging will help improve the success rate of initial closure and long-term continence rates.

The value of this research is two-fold. Firstly, the project will help us to verify if we are indeed dissecting down to the proper plane required for successful initial closure of bladder exstrophy. Secondly, this project will help others with relatively less experience with bladder exstrophy to properly identify where they are anatomically during closure of exstrophy, thus yielding higher success rates and better patient care.

## **2. Objectives**

### **2.1. The primary objectives of this research are:**

- a. To determine the safety and efficacy of the use the Brainlab, Inc. VisionVector® Cranial Image Guided Surgery System during closure of bladder exstrophy.
- b. To verify the proper plane of dissection during closure of bladder exstrophy using the VisionVector® Cranial Image Guided Surgery System by visualizing in real-time where the surgeon's instruments are relative to the levator muscles and confirming that the bladder is being placed in the most posterior and inferior location possible.

## **2.2. The secondary objectives of this trial are:**

- a. To improve the overall success rate of closure of bladder exstrophy as evidenced by lower rates of postoperative prolapse, dehiscence, and fistula formation as well as improved continence when compared with the current standard of care, which does not currently involve the use of image guided surgery.
- b. To decrease the learning curve for pediatric urology surgeons associated with closure surgery [6].

## **3. Background**

Other surgical fields, such as neurosurgery and otolaryngology, have successfully utilized stereotactic imaging technology to improve accuracy and success of surgical dissection and oncologic control through various procedures. This technology has resulted in less-invasive procedures with greater technical ease and confidence that the surgeon is truly in the correct anatomical location. The VectorVision Cranial Image Guided Surgery System (by Brainlab, Inc.) is an FDA-cleared device indicated for use in neurosurgery and otolaryngology as shown on the attached 510K summary. Several studies have been published demonstrating the safety and success of this device in stereotactic surgery [7].

The Cranial IGS system consists of the IGS workstation, the touch screen monitor and the optical 3D tracking system. It also includes a set of hardware accessories that provide for comfortable and accurate use of the system. The IGS workstation holds the patient data during the surgical procedure and runs the cranial software application. The patient data needed in order to perform the image guided surgery is acquired pre-operatively and is transferred to the IGS workstation via network, data carrier, or data bus.

The iPlan Cranial® allows for pre- and intraoperative stereotactic surgery planning based on stereotactic systems. Multiple graphical display functions and 3-dimensional views of anatomical structures offer effective and efficient means of presenting the anatomical data for diagnostic and surgical planning. Software application offers a display of the patient data in various reconstructions, segments and overlays on the touch screen monitor in addition to position information of tracked instruments. The touch screen monitor allows the control of the iPlan Cranial® software application and can be draped for sterile use by the surgeon. The optical 3D tracking system performs the localization of the patient and surgical tools within the operating field.

The virtual diagnostic image spaces are registered to the surgical environment by collecting the 3D position of anatomical landmarks with a tracked pointer probe and relating them with the corresponding features extracted from the diagnostic image data sets.

Intra-operatively acquired patient data can further be registered to the surgical environment by determining its spatial position in relation to the patient during its acquisition. Structures in the patient's body are localized using trackable pre-calibrated or intra-operatively calibrated surgical instruments such as the pointer probe. In addition to the pointer probe, various standard surgical equipment such as forceps and scissors can be calibrated and used for spatial positioning.

The Cranial IGS System contains a network based software interface that allows downloading medical data (such as image sets, objects, trajectories, or points) and tracking data from the system as well as uploading and displaying an image stream to the system. This interface can be used to implement custom visualization of medical data (e.g. included modalities which are otherwise unknown to the cranial software application) as well as to control other devices. These view data is strictly under the responsibility of the user and clearly marked as such.

Per the 510(k) clearances, these devices are currently indicated for adults and children with any medical condition where stereotactic surgery may be appropriate and where a reference to a rigid anatomical structure, such as a bone, can be identified relative to MRI or other similar imaging modality. The device has multiple utilities across various surgical fields and is routinely used in neurosurgery, spine surgery, and otolaryngology.

Studies from various institutions have demonstrated that successful outcomes in bladder exstrophy surgery rely upon proper anatomical dissection during surgery. Studies involving pre- and post-operative MRI have demonstrated this [8]. Furthermore, it has been well established that many bladder exstrophy closures fail because the bladder was not placed deep enough into the pelvis [5]. This is thought to be secondary to the surgeon's unfamiliarity with the patient's anatomy in this rare congenital anomaly, thus leading to placement of the bladder in a superficial plane, predisposing the patient to potential failed closure [9].

We propose to use this intraoperative stereotactic imaging system as a guide during the pelvic dissection in children ages 0-7 years that require closure of bladder exstrophy as we hypothesize that it will aid in identification and verification of the proper plane required for successful initial closure. Due to the nature of bladder exstrophy, this study cannot be done on adults. However, according to multiple studies, image guided surgery can be as safe and beneficial in the pediatric population as it has shown to be in adults [10-11]. We expect that, as seen with applications in other various fields, the use of image-guided surgery will allow for improved visualization and accurate navigation of the planned surgery [10, 12-13]. Additionally, the use of image-guided surgery should allow the possibility of extending the pelvic dissection safely in order to place the bladder in closer proximity to the puborectalis and levator ani muscles, allowing these muscles to aid in increasing bladder capacity postoperatively and ultimately increasing the rate of successful exstrophy closure and urinary continence [14]. We also expect that the use of image-guided surgery will result in a similar reduction in morbidity and mortality as well as a shortening of hospital stay.

#### **4. Study Procedures**

##### **4.1. Study design**

This is a prospective, single arm, interventional trial of 60 subjects aged 0-7 years who require bladder exstrophy closure as part of routine medical care.

##### **a. Minimizing Bias**

Blinding is not applicable to this study design. The surgery and management of this procedure will be carried out exactly as in standard clinical practice with the exception of adding confirmatory intra-operative stereotactic imaging. As such, a placebo group or non-treatment group is not applicable to this study.

##### **b. Treatment Failure/Patient Removal**

This study does not involve any change to specific disease treatment, so treatment failure definition is not appropriate for this trial. A patient may be removed from the study based on the wishes of their parent/guardian or if a member of the designated group of faculty in charge of safety monitoring (outlined in section 11) feels that the safety of the patient is jeopardized by the new intervention. Studies show that as high as 63% of closures fail [15]. The designated faculty will work to determine if the treatment failures are a result of this designated intervention and if so patients will be withdrawn. Any data collected up to the date of patient/guardian withdrawal of consent will be kept and included in study analyses. Any patients removed from study will be replaced.

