## **9.2. Risks Specific to Research Activities**

Soft tissue distortion that occurs during surgery or inaccuracies during registration of the virtual diagnostic images described in section 6.5 may cause the virtual image to misrepresent the patient's actual anatomy. However, this poses minimal risk to the patient as the image guidance will only be used as a supplement to direct visual inspection of patient's anatomy by the surgeon and will not be used as the primary source for visual guidance into the operating field.

Another risk is the possibility that the external fixator pins described in section 6.5 may shift from their original placement while applying the VectorVision® 2-pin fixator. Though this risk is unlikely, if this were to happen corrective measures would be taken to restore the

external fixator pins back to their appropriate position prior to continuation of the procedure.

Just as with use of any computerized equipment, there is a risk of equipment malfunction that may result in an increase in operating time. Overall, known risks are rare, but these and any unanticipated problems will be medically managed as appropriate, and reported to the IRB and FDA promptly as per DSMP.

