## 11. Data and Safety Monitoring Plan

The research involves some risks to the participants. A group of designated faculty, that includes Pediatric Orthopedic Surgeon [name], Pediatric Anesthesiologist [name], and Adult Urologist [name] [name], will be involved in safety monitoring. These individuals will be notified promptly for any serious adverse events or deaths and will perform routine monitoring and oversight reviews of the research and postoperative outcomes to assess for trends or risks that were not previously identified. In the event of an adverse event, unanticipated problem, or a study deviation the IRB will be notified within 24-48 hours and the research will be halted pending review. Per the Johns Hopkins IRB policy 103.6b, "Unanticipated problems involving risks to participants or others" is defined as: The information is unexpected in terms of nature, severity, or frequency, given:

- a. The research procedures described in the protocol and informed consent document; and
- b. The characteristics of the subject population being studied; and
- c. The information indicates that participants or others are at greater risk of harm (including physical, psychological, economic, or social harm) than was previously known or recognized.

Also as per policy, the prompt reporting of unanticipated problems or events will occur as soon as possible after the PI learns of the event, but in all cases within 10 working days with the exception of death of a participant which must be reported within 3 working days.

Additionally, a team of designated faculty, including the PI's clinical fellow, the orthopedic surgeon ([name]), and the radiologist ([name]), will be present to monitor the patient during surgery. Standard safety monitoring by the anesthesiology team during surgery and post-operative nursing staff will monitor the patient for any safety concerns related to the surgery or immediate post-operative care.

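### Section 4.1b relies on case verdicts about device-caused closure failures; it should keep every device-guided closure in a cumulative all-cause failure count set beside a named reference rate

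*Combined protocol and SAP*

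**What the plan says.** Section 4.1b states that a definition of treatment failure is not appropriate for this trial. It then gives a background figure, "Studies show that as high as 63% of closures fail", and a task: "The designated faculty will work to determine if the treatment failures are a result of this designated intervention". A positive finding leads to withdrawal of the patient, and anyone removed is replaced. The sentence on keeping data covers data collected before a patient or guardian withdraws consent. It does not mention patients withdrawn by the faculty.

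Section 4.1 describes the design: "This is a prospective, single arm, interventional trial of 60 subjects aged 0-7 years". Under Minimizing Bias, "a placebo group or non-treatment group is not applicable to this study".

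Section 3 says of surgery without the device that "many bladder exstrophy closures fail because the bladder was not placed deep enough into the pelvis". Section 9.2 concedes that tissue distortion or registration error "may cause the virtual image to misrepresent the" true anatomy of the child.

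Other sections give a group view. Closure success or failure is a primary outcome in 4.3. It is collected quarterly for 12 months (sections 5 and 11.5), and 11.5 defines failure as dehiscence, prolapse or vesicocutaneous fistula, without regard to cause. Sections 8.3 and 11.5 compare outcomes with published or established rates, which they do not state. Section 11 gives the designated faculty "routine monitoring and oversight reviews of the research and postoperative outcomes to assess for trends", with no schedule, table or benchmark. Section 8.3 plans no formal tests and 8.4 has no early stopping rules.

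**The concern.** Failed closure is a main route by which a navigation error could harm a child. If a misleading image leaves the bladder too superficial, the expected result is the same dehiscence, prolapse or fistula that the protocol says occurs without the device. With no concurrent control, a reviewer looking at one such failure often has little to separate the two causes. A modest rise in the failure rate could then be judged one case at a time without being seen as a rise.

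The second problem is bookkeeping. The verdict triggers withdrawal and replacement, and the text does not say whether a failure withdrawn on that ground stays in the analysed count. If it did not, the failures thought most likely to be due to the device would be the ones to leave the failure rate.

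**Working it through.** **Inputs.** From the documents: n = 60, a single arm, and a background failure rate of up to 63%. Assumed, because the plan names no other rate: backgrounds p0 of 10%, 20% and 30%, and a true rise of 10 points. The plan has no figure to reproduce, since 60 was set from yearly case volume without a power calculation.

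**Step 1: what the rates alone say about one failure.** The share of failures in excess of background is (p1 − p0)/p1.

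- p0 = 10%, p1 = 20%: 0.10/0.20 = 50%
- p0 = 20%, p1 = 30%: 0.10/0.30 = 33%
- p0 = 30%, p1 = 40%: 0.10/0.40 = 25%
- p0 = 63%, p1 = 73%: 0.10/0.73 = 14%
- p0 = 63%, p1 = 100%: 0.37/1.00 = 37%

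In each 10-point case the expected number of extra failures is 60 × 0.10 = 6. These shares describe a reviewer with no case-specific evidence.

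**Step 2: what a cumulative count would show at n = 60.** Take the smallest count r whose exact (Clopper-Pearson) 95% lower limit exceeds p0, then the binomial chance of reaching r.

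| p0 | r | chance if true rate = p0 | chance if true rate = p0 + 10 points |
|---|---|---|---|
| 10% | 12 | 0.015 | 0.55 |
| 20% | 19 | 0.022 | 0.44 |
| 30% | 26 | 0.020 | 0.34 |
| 63% | 46 | 0.017 | 0.32 |

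For a 20-point rise the chances are 0.97, 0.93, 0.88 and 0.93. Early on the count says less. With p0 = 10% and a true rate of 20%, the chance is 0.16 at n = 15 (r = 5) and 0.22 at n = 25 (r = 7). The 25 matters because section 4.2 also gives 25 as the expected enrolment, which conflicts with 60. All these chances are for a single look.

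**Step 3: what removal could do to the count.** Suppose 12 of 60 closures fail: 20%, exact 95% interval 10.8% to 32.3%. Suppose also that 4 of the 12 are judged device-related, leave the analysis and are replaced by 4 children without failure. The count becomes 8 of 60: 13.3%, interval 5.9% to 24.6%. The lower limit is now below 10%. This illustrates what the silence in 4.1b permits; the protocol does not say that it will happen.

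**The case against.** The sentence in 4.1b is a rule for removing patients. It does not say that a failure judged unrelated is ignored, and it speaks of failures in the plural; review of each case is inferred from the consequence, which falls on the individual patient. Closure failure is recorded for every child whatever its cause, compared with established rates and reviewed for trends. All of this stands, and it rules out the stronger reading that the plan has no group view of failures. What is missing is a reference rate, a fixed table and a statement of who is counted.

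A reader might also infer that no failure could ever be attributed to the device, because at a 63% background the excess share cannot pass 37%. The documents do not support that. The 63% is an upper figure and, by its title, the cited study covers children presenting late or after a failed closure. At an assumed 10% background the share reaches 50%. Reviewers will also have case evidence: landmark registration (section 5), a check of visible structures against the virtual image (9.5), a radiologist and an orthopedic surgeon present (section 11), and possibly a visible registration error or pin shift (9.2). If the device prevents some failures while causing others, the excess share understates causation.

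Nor do the documents show that verdicts would lean towards clearing the device. Section 4.1b sets no probability standard, and under 11.5 a possible relation is enough for an adverse event to be collected.

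Finally, the count is no strong detector: for a 10-point rise it misses more often than it responds at backgrounds of 20% and above. That objection stands, and limits what the change can promise.

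**Conclusion.** The point holds in a limited form. Case verdicts alone are a weak way to detect an excess of closure failures in this single-arm design, and 4.1b leaves open whether failures withdrawn on such a verdict stay in the analysis. With an assumed 10-point rise, 50% to 14% of failures would be excess across backgrounds of 10% to 63%, with 6 extra failures expected in 60. A cumulative count would place its lower limit above the reference with probability 0.55 to 0.32. The backgrounds of 10% to 30% and the size of the rise are assumptions.

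It would go too far to say that the protocol discards device-related failures, or that an excess would go unseen. The text is silent on the first, and the trend review could reveal the second. This is a cheap improvement to the monitoring text.

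**What to change.** State in 4.1b and section 11 that every device-guided closure stays in both numerator and denominator, whatever the presumed cause and whether or not the child is later withdrawn or replaced. Keep the faculty's case-level opinion as a recorded note that does not decide whether a failure counts.

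At each quarterly review, give the designated faculty one row: cumulative failures (11.5 definition) over all device-guided closures to date, with an exact 95% interval, beside a no-device reference rate. Name that rate and its source in 8.3, for a population comparable with the children enrolled.

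Reconcile the statement in 4.1b that a failure definition is not appropriate with the definition in 11.5. The rule for withdrawing patients is left to the sponsor.

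The cost is protocol wording, the choice of a reference rate, and one table row from data already collected quarterly. Early intervals will be wide. Repeated looks are descriptive only, since no adjustment is made for them, and an interval that includes the reference rate is not evidence of no harm.

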#### **4.3. Study Outcomes**

##### **a. Primary Outcomes**

The primary outcomes for this trial are success or failure of exstrophy closure, urinary continence, operative time, length of hospital stay, and a record of all peri-operative and post-operative complications

##### **b. Secondary Outcomes**

The secondary outcome for this trial is improved identification of the pelvic floor anatomy during bladder exstrophy closure as reported subjectively by the surgeon at the time of surgery.

#### **4.4. Recruitment Information**

The PI will be responsible for approaching parents/guardians of potential participants. Potential participants will be identified and assessed for potential eligibility for study inclusion at the time of their routine Pediatric Urology clinic visits or inpatient consultations when their operative procedure is scheduled. Patients will be approached for possible inclusion in this study once the patient’s parents or legally authorized representative (LAR) have already decided to have the patient undergo the respective operative procedure.

#### **4.5. Informed Consent**

The PI and IRB approved study co-investigators will be responsible for conducting the informed consent discussions with the parents/LAR of potential participants. Discussions regarding study participation will take place in private areas after the patient and their parent/LAR have already decided to undergo the respective operative procedure. Enrollment in this research study will be presented as optional and purely voluntary. All risks of the study will be discussed. Parents or the legally authorized representative will be provided with the IRB approved consent form at their clinic visit or initial consultation. Patients or the LAR will be given as much time as needed to consider study participation. As many visits as necessary will be provided. The informed consent will be collected from those wishing to participate at a clinic visit or consultation prior to surgery or on the morning of the operative procedure

Competency to comprehend informed consent both for the research study will be assessed by the investigator. Only parents/legally authorized representatives of patients that are able to understand the consent form and comprehend the nature of the procedure will be enrolled.

